9. OTHER STATISTICAL ANALYSES

9.1. Exploratory Pharmacodynamic and Biomarker Analyses

9.1.1. Overview of Planned Exploratory Pharmacodynamic and Biomarker Analyses

The pharmacodynamic analyses will be based on the Safety population, unless otherwise specified.

Table 9 provides an overview of the planned pharmacodynamic and Biomarker analyses, with full details of data displays being presented in [Appendix 8: List of Data Displays](#).

Table 10 Overview of Planned Exploratory Pharmacodynamic and Biomarker Analyses

Endpoint	Untransformed				
	Absolute				
	Summary		Individual		
	T	F	L	F	
Skin Biopsy					
IFN proteins (e.g. MxA, CXCL10) in skin biopsies	Y ^{2,3}	Y ³	Y ²	Y ³	
Immune cell proteins (e.g. CD3, CD20, CD11c, CD123, CD68) in skin biopsies	Y ^{2,3}	Y ³	Y ²	Y ³	
Histopathology score in skin biopsies ^[1]	Y ^{2,3}	Y ³	Y ²	Y ³	
pSYK and SYK protein in skin biopsies	Y ^{2,3}	Y ³	Y ²	Y ³	

NOTES :

- T = Table, F = Figure, L = Listing, Y = Yes display generated.
- Stats Analysis = Represents TFL related to any formal statistical analyses (i.e. modelling) conducted.
- Summary = Represents TFL related to any summaries (descriptive statistics) of the observed raw data.
- Individual = Represents FL related to any displays of individual subject observed raw data.
- [1] component scores; parakeratosis, ballooning/hydropic degeneration, epidermal cell-death, junctional and dermal inflammation will not be statistically analysed.
- [2] Include both absolute and change from baseline
- [3]: By Disease Characteristics (Chronic CLE, Acute CLE, Sub-acute CLE, LET and All).

11. APPENDICES

Section	Appendix
RAP Section 5 : General Considerations for Data Analyses & Data Handling Conventions	
Section 11.1	Appendix 1 : Time and Events
Section 11.2	Appendix 2 : Data Display Standards & Handling Conventions 
 • Study Treatment & Sub-group Display Descriptors • Baseline Definitions & Derivations • Reporting Process & Standards
Section 11.3	Appendix 3 : Derived and Transformed Data 
 • General, Study Population & Safety • Efficacy • Pharmacodynamic and or Biomarkers
Section 11.4	Appendix 4 : Premature Withdrawals & Handling of Missing Data 
 • Premature Withdrawals • Handling of Missing Data
Section 11.5	Appendix 5 : Values of Potential Clinical Importance
Section 11.6	Appendix 6 : Model Checking and Diagnostics for Statistical Analyses
Other RAP Appendices	
Section 11.7	Appendix 7 : Abbreviations & Trade Marks
Section 11.8	Appendix 8 : List of Data Displays
Section 11.9	Appendix 9 : Example Mock Shells for Data Displays

11.1. Appendix 1: Time & Events

11.1.1. Protocol Defined Time & Events

11.1.2. Group A

Procedure	Screening (up to Day - 28)	Day -15	Day -14	Day - 13 to - 1	Day 1	Day 2 to Day 13	Day 14	Day 15 to Day 20	Day 21 to Day 27	Day 28	Day 29 to 42	Follow- up ^a	^a All procedures listed to also be conducted if a subject decides to prematurely withdraw/discontinue
Informed Consent	X												
Inc/Exc criteria assessment	X												
Demography	X												
Pregnancy Test (women)	X				X			X				X	Pregnancy testing to be performed at Screening, on Day 1 (pre-dose), Day 14 (pre-dose) and once during follow-up, with day recorded
TSH, free T4, free T3	X				X		X					X	
Vital Signs	X	X			X		X			X			
Safety Lab Samples (clin chem, haematol, Urinalysis)	X	X		X	X		X			X		X	On days of dosing samples should be taken predose. Sample timepoints during the Day-13 to Day-1 period are as follows: – once weekly during visits to assess PV lesion development
Full Physical Exam	X											X	

CONFIDENTIAL

204860

Procedure	Screening (up to Day - 28)	Day -15	Day -14	Day - 13 to - 1	Day 1	Day 2 to Day 13	Day 14	Day 15 to Day 20	Day 21 to Day 27	Day 28	Day 29 to 42	Follow- up ^a	^a All procedures listed to also be conducted if a subject decides to prematurely withdraw/discontinue
Brief Physical Exam				X									Assessment to be performed pre-dose Sample timepoints during the Day-13 to Day-1 period are as follows: – once weekly during visits to assess PV lesion development
12-lead ECG	X				X		X					X	On days of dosing assessments should be performed pre-dose
SLE clinical assessment	X				X					X		X	On days of dosing assessment as defined by the investigator to be performed pre-dose .
ANA, anti-dsDNA, anti-Ro and anti-La antibodies, HIV, Hep B, Hep C, FSH, Drug screen	X												
Skin Biopsies					X ^b					X ^b			^b Day 1 biopsies will be taken pre-dose. Day 28 biopsies will be taken 4 hours post-dose
UV threshold testing		X											
Photoprovocation				X ^{c, d}									Performed 24 hours after UV threshold testing. ^c PV occurs once every 24 hours for 3 days on Day-14, Day-13 & Day-12. ^d If PV induced lesions appear at all 3 sites after Day -14 or Day -13, PV treatment can be stopped early

CONFIDENTIAL

204860

Procedure	Screening (up to Day - 28)	Day -15	Day -14	Day - 13 to - 1	Day 1	Day 2 to Day 13	Day 14	Day 15 to Day 20	Day 21 to Day 27	Day 28	Day 29 to 42	Follow- up ^a	^a All procedures listed to also be conducted if a subject decides to prematurely withdraw/discontinue
Lesion induction assessment			<----X---->										
Lesion resolution assessment											X	X	
Clinical score				X		X				X			Components of the RCLASI as defined in Section 11.3.4 Assessments to be performed pre-dose
Local Tolerability Assessment				X	X	X	X	X	X	X			Assessments to be performed pre-dose and up to one hour following dosing on days of dosing
Dosing				X	X	X	X	X	X	X			Once daily
Randomisation				X									Pre-dose

CONFIDENTIAL

204860

Procedure	Screening (up to Day - 28)	Day -15	Day -14	Day - 13 to - 1	Day 1	Day 2 to Day 13	Day 14	Day 15 to Day 20	Day 21 to Day 27	Day 28	Day 29 to 42	Follow-up ^a	^a All procedures listed to also be conducted if a subject decides to prematurely withdraw/discontinue
PK blood sample				X	X	X			X	X	X	X	Sampling timepoints: Day 1 = pre-dose; and 5hrs (± 1 hr) Between Day 2 and Day13: one pre-dose sample or postdose sample with time recorded since last dose Day 14: predose sample Between Day 21 and Day27: one pre-dose sample or postdose sample with time recorded since last dose Day 28: one postdose sample with time recorded since last dose Between Day 29 and Day 42: one sample with time recorded since last dose Follow-up visit: one sample with sampling day recorded
AE/SAE Review	X	<-----X----->											
Concomitant Medication Review	X	<-----X----->											

11.1.3. Group A PV non-responders

Procedure	Once-weekly up to 28 days after first photoprovocation	Final Follow-up visit(s) (occurs until final PV induced lesion has resolved)	Notes
Brief Physical Exam	X	X	IMPORTANT: This table is ONLY applicable for subjects in group A that do not develop PV induced lesions within 14 days of the start of photoprovocation. Once-weekly assessments will occur from 15 days post first photoprovocation up until 28 days post first photoprovocation. Any PV lesion that develops after 15 days post-photoprovocation will be followed up until resolution.
PV Lesion assessment (if present)	X	X	
AE/SAE Review	X	X	
Concomitant Medication Review	X		

11.1.4. Group B

Procedure	Screening (up to Day -28)	Day -5 to -3	Day 1	Day 2 to Day 13	Day 14	Day 15 to Day 20	Day 21 to Day 27	Day 28	Day 29 to 42	Follow-up (between Day 43 to Day 56) ^a	^a All procedures listed to also be conducted if a subject decides to prematurely withdraw/discontinue
Informed Consent	X										
Inc/Exc criteria assessment	X										
Demography	X										
Pregnancy Test (women)	X		X		X				X	Pregnancy testing to be performed at Screening, on Day 1 (pre-dose), Day 14 (pre-dose) and once during follow-up, with day recorded	
TSH, free T4, freeT3	X		X		X				X		
Vital Signs	X	X			X			X			
Safety Lab Samples (clin chem ,haematol, Urinalysis)	X	X	X		X			x	X	On days of dosing samples should be taken predose	
Full Physical Exam	X								X		
Brief Physical Exam			X							Assessment to be performed pre-dose	
12-lead ECG	X		X		X				X	On days of dosing assessments should be performed predose	
SLE clinical assessment	X		X					X	X	On days of dosing assessment as defined by the investigator to be performed pre-dose .	
ANA, anti-dsDNA antibodies, anti-Ro and anti-La antibodies, HIV, Hep B, Hep C, FSH, Drug screen	X										
Lesion selection		X									

CONFIDENTIAL

204860

Procedure	Screening (up to Day -28)	Day -5 to -3	Day 1	Day 2 to Day 13	Day 14	Day 15 to Day 20	Day 21 to Day 27	Day 28	Day 29 to 42	Follow-up (between Day 43 to Day 56) ^a	^a All procedures listed to also be conducted if a subject decides to prematurely withdraw/discontinue
Skin Biopsies		X ^b						X ^b			^b 2 to 4 days healing time will be allowed prior to randomisation and the first dose. Day 28 biopsies will be taken 4 hours post-dose
Clinical score			X		X			X			
Local tolerability Assessment			X	X	X	X	X	X	X		Assessments to be performed pre-dose and up to one hour following dosing on days of dosing
Dosing			X	X	X	X	X	X			Once daily
Randomisation			X								Pre-dose

CONFIDENTIAL

204860

Procedure	Screening (up to Day -28)	Day -5 to -3	Day 1	Day 2 to Day 13	Day 14	Day 15 to Day 20	Day 21 to Day 27	Day 28	Day 29 to 42	Follow-up (between Day 43 to Day 56) ^a	^a All procedures listed to also be conducted if a subject decides to prematurely withdraw/discontinue
PK blood sample			X	X	X		X	X	X	X	
Sampling timepoints: Day 1 = pre-dose; and 5hrs (± 1 hr)
 
Between Day 2 and Day13: one pre-dose sample or postdose sample with time recorded since last dose
 
Day 14: predose sample
 
Between Day 21 and Day27: one pre-dose sample or postdose sample with time recorded since last dose
 
Day 28:one postdose sample with time recorded since last dose
 
Between Day 29 and Day 42: one sample with time recorded since last dose
 
Follow-up visit: one sample with sampling day recorded

AE/SAE Review						X					
Concomitant Medication Review						X					
Lesion resolution assessment								X	X		

11.2. Appendix 2: Data Display Standards & Handling Conventions

11.2.1. Study Treatment & Sub-group Display Descriptors

Study population and Safety displays will be presented by sequence. Treatment will not be used to summarise these endpoints as all subjects will receive both active and placebo concurrently.

Study Group Descriptions			
RandAll NG		Data Displays for Reporting	
Strata Code	Description	Description	Order [1]
A	Group A - Fewer than 2 active lesions (PV)	Group A - (PV lesions)	1
B	Group B - At least 2 active CLE lesions	Group B – (CLE lesions)	2

Group A sequence descriptions:

Sequence Descriptions			
RandAll NG		Data Displays for Reporting	
Code	Description	Description	Order [1]
AA/PC/AD	GSK2646264 skin site A/ Placebo skin site C/ GSK2646264 skin site D	GSK2646264 skin area A/ Placebo skin area C/ GSK2646264 skin area D	1
AA/PC/PD	GSK2646264 skin site A/ Placebo skin site C/ Placebo skin site D	GSK2646264 skin area A/ Placebo skin area C/ Placebo skin area D	2
PA/AC/AD	Placebo skin site A/ GSK2646264 skin site C/ GSK2646264 skin site D	Placebo skin area A/ GSK2646264 skin area C/ GSK2646264 skin area D	3
PA/AC/PD	Placebo skin site A / GSK2646264 skin site C/ Placebo skin site D	Placebo skin area A/ GSK2646264 skin area C/ Placebo skin area D	4

NOTES:

1. Order represents treatments being presented in TFL, as appropriate.
2. Present code as well as description in displays

Group B sequence descriptions:

Sequence Group Descriptions			
RandAll NG		Data Displays for Reporting	
Code	Description	Description	Order ^[1]
AF/PG	GSK2646264 skin site F/ Placebo skin site G	GSK2646264 skin area F/ Placebo skin area G	1
PF/AG	Placebo skin site F/ GSK2646264 skin site G	Placebo skin area F/ GSK2646264 skin area G	2

NOTES:

1. Order represents treatments being presented in TFL, as appropriate.
2. Present code as well as description in displays.

Based on the randomisation schedule, treatments/descriptions will be programmatically assigned to each skin site area. Local tolerability, Efficacy and Pharmacodynamic endpoints are measured at a skin site level and therefore the following treatments will be used:

Group A

Treatment group descriptions			
Skin area		Data Displays for Reporting	
Code	Type	Description	Order
A	PV lesion	GSK2646264 or Placebo ^[2]	1 or 2
B	PV lesion	Baseline lesion	3
C	PV lesion	GSK2646264 or Placebo ^[2]	1 or 2
D	Uninvolved Skin	GSK2646264 or Placebo ^[2]	1 or 2
E	Uninvolved Skin	Uninvolved skin	4

NOTES:

1. Order represents treatments being presented in TFL, as appropriate.
2. Based on randomisation schedule
3. GSK2646264 will have a code of 1, Placebo will have a code of 2

Group B

Treatment group descriptions			
Skin area		Data Displays for Reporting	
Code	Type	Description	Order
F	Natural Lesion	GSK2646264 or Placebo ^[2]	1 or 2
G	Natural Lesion	GSK2646264 or Placebo ^[2]	1 or 2
H	Uninvolved Skin	Uninvolved skin	4

NOTES:

1. Order represents treatments being presented in TFL, as appropriate.
2. Based on randomisation schedule
3. GSK2646264 will have a code of 1, Placebo will have a code of 2

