### 6. STUDY TREATMENT

The term 'study treatment' is used throughout the protocol to describe any combination of products received by the subject as per the protocol design. Study treatment may therefore refer to the individual study treatments or the combination of those study treatments.

Study Treatment		
Product name:	1% GSK2646264	Placebo
Formulation description:	White to off white aqueous cream	White to off white aqueous cream
Dosage form:	Topical	Topical
Unit dose strength(s)/Dosage level(s):	1% (w/w)	NA
Route/ Administration/ Duration:	Topical	Topical
Dosing instructions:	Should be applied topically as directed.	Should be applied topically as directed.
Physical description:	White-to-off-white aqueous cream stored in amber glass jars	White-to-off-white aqueous cream stored in amber glass jars
Manufacturer/ source of procurement:	Medpharm Guildford	Medpharm Guildford

[figure not shown]

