## 6.1. Treatment Assignment

Subjects will be assigned to treatment in accordance with the randomisation schedule generated by Clinical Statistics, prior to the start of the study, using validated internal software.

Skin areas A-C in group A are horizontally distributed across the back of the patient. The PV lesions will be labelled A, B, C. Study drug and placebo will be randomly assigned to lesions A and C. Lesion B will not be assigned a treatment and will be used for the baseline skin biopsy. A further area of uninvolved skin (area D) will also be treated with study drug or placebo in a ratio of 4:1. Another area of uninvolved skin (area E) will not be treated with either study drug or placebo and will be used solely to take a baseline biopsy.

Lesion/Skin Area	Type	Biopsy timing	Receives Drug/Placebo
A	PV lesion	Day 28	✓
B	PV lesion	Baseline	
C	PV lesion	Day 28	✓
D	Uninvolved Skin	Day 28	✓
E	Uninvolved Skin	Baseline	

**Figure 1 Approximate anatomical representation of UV lesion induction sites (A-C) and uninvolvled skin (D and E) for Group A**

Group A subjects will be assigned to the following regimens:

	Skin Sites A/C/D	Assignment ratio
Sequence 1	A/P/A	4
Sequence 2	A/P/P	1
Sequence 3	P/A/A	4
Sequence 4	P/A/P	1

P=Placebo, A= GSK2646264 1%

The nurse administering the treatments may be aware whether a patient is assigned to sequences 1/4 or sequences 2/3, however they will remain blinded to treatment.

In group B, at the day -5 to day -3 visit, prior to pre-dose biopsies being taken, the two chosen lesions will be labelled F and G based on size (F >G). The two lesions will be randomly assigned placebo or study drug. An area of uninvolvled skin (area H) will not

be treated with either study drug or placebo and will be used solely to take a biopsy at baseline. These lesions can be on any part of the body (all 3 lesions must be in the same anatomical area), but the subject must consent to be biopsied from the area with the lesions.

Lesion/Skin Area	Skin Type	Biopsy timing	Receives Drug/Placebo
F	Natural lesion	Baseline and Day 28	✓
G	Natural lesion	Baseline and Day 28	✓
H	Uninvolved Skin	Baseline	

Group B subjects will be assigned to one of the following regimens:

	Skin Sites F/ G	Assignment ratio
Sequence 1	A/P	1
Sequence 2	P/A	1

P=Placebo, A= GSK2646264 1%

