### **9.2. Sample Size Considerations**

There are no formal calculations of power or sample size for this study. The sample sizes have been chosen based on feasibility, to primarily allow the assessment of safety and tolerability of GSK2646264 in patients with CLE.

[figure not shown]
We will recruit approximately 25 patients with CLE into the study with the aim to randomise approximately 20 patients. Approximately 10 patients will undergo PV in group A. PV response rates are estimated at 50% and we expect up to 5 PV positive patients to be randomised into the study. We aim to randomise approximately 15 patients into group B of the study. All patients will be treated with both GSK2646264 and placebo on separate lesions (see Section 6.1 for details).

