#### **9.2.1. Sample Size Assumptions**

There are no formal calculations of power or sample size for this study. The sample sizes have been chosen based on feasibility.

The primary objective of the study is safety, where a number of safety events are of interest.

For group A, Using a Bayesian approach to determine the confidence interval around an observed safety event, we would assume a flat Beta (1,1) prior, and if we were to observe 1 safety event in 5 then the posterior distribution would be Beta (2, 5), as outlined below:

[figure not shown]
Where we can be 95% certain that the true probability of the safety event lies between 0.04 and 0.64.

A sample size sensitivity analysis has been conducted on the primary endpoint, to investigate different safety event rates with 5 subjects in part A. Additionally, if the number of subjects is lower than 5 in group A, then the true incidence rates of safety events that could not be ruled out would change.

These changes are outlined in the table below:

N completing the study	Number of particular safety events observed with active	Upper limit of exact 95% CI indicating that a true incidence rate of x% could not be ruled out
5	0	46%
5	2	78%
4	0	52%
4	1	72%
4	2	85%

For group B, using a Bayesian approach to determine the confidence interval around an observed safety event, we would assume a flat Beta (1,1) prior, and if we were to observe 1 safety event in 15 then the posterior distribution would be Beta (2, 15), as outlined below:

Where we can be 95% certain that the true probability of the safety event lies between 0.02 and 0.30.

A sample size sensitivity analysis has been conducted on the primary endpoint, to investigate different safety event rates with 15 subjects in part B. Additionally, if the number of subjects is lower than 15 in group B, then the true incidence rates of safety events that could not be ruled out would change.

These changes are outlined in the table below:

N completing the study	Number of particular safety events observed with active	Upper limit of exact 95% CI indicating that a true incidence rate of x% could not be ruled out
15	0	21%
15	2	38%
12	0	25%
12	1	36%
12	2	45%

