11.8.5. Safety Tables

Safety : Tables					
No.	Population	IDSL / TST ID / Example Shell	Title	Programming Notes	Deliverable [Priority]
Adverse Events					
2.1.	Safety	CP_AE1p	Summary of All Adverse Events by System Organ Class (Group B-Natural Lesions)	Only Total adverse events will be summarised.	SAC
2.2.	Safety	CP_AE1p	Summary All Drug-Related Adverse Events by System Organ Class (Group B-Natural Lesions)	Only Total adverse events will be summarised.	SAC

Safety : Tables					
No.	Population	IDSL / TST ID / Example Shell	Title	Programming Notes	Deliverable [Priority]
Serious and Other Significant Adverse Events					
2.3.	Safety	CP_AE1p	Summary of Serious Adverse Events by System Organ Class (Group B-Natural Lesions)	Only Total adverse events will be summarised.	SAC
2.4.	Safety	CP_AE1p	Summary of Adverse Events Leading to Withdrawal from Study / Permanent Discontinuation of Study Treatment by Overall Frequency (Group B-Natural Lesions)	Only Total adverse events will be summarised.	SAC
Laboratory: Chemistry					
2.5.	Safety	LB1	Summary of Chemistry Changes from Baseline (Group B-Natural Lesions)	Treatment column will not be displayed.	SAC
2.6.	Safety	LB3	Summary of Emergent Chemistry Results Relative to Normal Range (Group B-Natural Lesions)	Treatment columns will be replaced by one 'Part B' column	SAC
Laboratory: Hematology					
2.7.	Safety	LB1	Summary of Hematology Changes from Baseline (Group B-Natural Lesions)	Includes baseline values. Treatment column will not be displayed.	SAC
2.8.	Safety	LB3	Summary of Emergent Hematology Results Relative to Normal Range (Group B-Natural Lesions)	As notes for Chemistry T2.12.	SAC
Laboratory: Urinalysis					
2.9.	Safety	LB1	Summary of Urine Concentration Changes from Baseline (Group B-Natural Lesions)	Includes Baseline values. Treatment column will not be displayed.	SAC
2.10.	Safety	LB2	Summary of Emergent Urinalysis Dipstick Results (Group B-Natural Lesions)	As above for Chemistry, using dipstick categories.	SAC
Laboratory: Hepatobiliary (Liver)					
2.11.	Safety	LIVER1	Summary of Liver Monitoring/Stopping Event Reporting (Group B-Natural Lesions)	Treatment columns will be replaced by one 'Part B' column	SAC

Safety : Tables					
No.	Population	IDSL / TST ID / Example Shell	Title	Programming Notes	Deliverable [Priority]
2.12.	Safety	LIVER10	Summary of Subjects Meeting Emergent Hepatobiliary Laboratory Abnormality Criteria (Group B-Natural Lesions)	Treatment columns will be replaced by one 'Part B' column	SAC

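### Application-site adverse events are reported without lesion or treatment, although each treated lesion has a known randomised cream

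*SAP*

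**What the plan says.** **Design.** Protocol 9.2: "All patients will be treated with both GSK2646264 and placebo on separate lesions". For Group B, Protocol 6.1 adds: "The two lesions will be randomly assigned placebo or study drug", using two sequences in equal ratio on lesions F and G. On numbers, Protocol 9.2 says "We aim to randomise approximately 15 patients into group B of the study". SAP 2.1 records that nobody was randomised in Group A, so the AE summary tables cover Group B only.

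**Primary endpoint.** Protocol 3 and SAP 2.2 assess safety and tolerability through laboratory tests, vital signs, ECG and AE reporting. The lesion-level irritation score is not in that list.

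**Displays.** SAP 11.2.1 first says safety displays will be by sequence, then: "Treatment will not be used to summarise these endpoints as all subjects will receive both active and placebo concurrently". Later in the same section it makes an exception: "Local tolerability, Efficacy and Pharmacodynamic endpoints are measured at a skin site level", and these are shown by treatment, assigned from the randomisation schedule. In SAP 11.8.5 each of AE Tables 2.1 to 2.4, including the drug-related Table 2.2, carries the note "Only Total adverse events will be summarised". In SAP 11.8.12, AE Listings 14, 18 and 20 have no treatment heading and Listing 16 has no treatment column.

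**Causality.** Under Protocol 12.3.5 the investigator judges each AE against study treatment. Protocol 6 lists both creams under that term and says: "Study treatment may therefore refer to the individual study treatments or the combination of those study treatments".

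**Precision.** The tables in Protocol 9.2.1 are indexed by "Number of particular safety events observed with active".

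**The concern.** The SAP gives one reason for dropping treatment, that both creams are applied at once, and applies it to every AE. That reason depends on the type of event. A headache or a raised ALT cannot be assigned to one of two creams used on the same day. Burning on lesion F can, because the cream on F is fixed by the randomisation schedule.

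At stake is a randomised, within-patient display of local AEs for a topical product. Vehicle reactions are a realistic possibility here: the risk table in Protocol 4.6.1 reports transient erythema in the minipig with vehicle as well as with test article. As planned, a local AE on the placebo lesion and one on the active lesion look the same in every AE table, and no AE display is specified to show the lesion.

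**Working it through.** **1. Which safety data can be tied to one cream?**

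| Data | Tied to one cream? | Planned display |
|---|---|---|
| Laboratory, ECG, vital signs | No | One Group B column, or no treatment column |
| Systemic AEs | No | Totals |
| Application-site AEs | Yes, if the lesion is known | Totals |
| Irritation score, dermal response, other effects | Yes | By treatment: Tables 2.19 and 2.20, Listing 35 |

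Only the third row is handled in a way that the design does not force.

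**2. Tracing a local AE on the placebo lesion.** The investigator judges it against study treatment, which covers either cream, in a double-blind trial. If it is judged related, it qualifies for Table 2.2. That table has no split by treatment, lesion or sequence.

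**3. What the scored assessments cover.** The scale in Protocol 5.4.2 records visible signs: erythema, oedema, papules, vesicles, spread, glazing, fissures, exudate and erosions. It has no item for itch, burning or pain. On dosing days it is taken before dosing and up to one hour after (Protocol 7.1.3). A score carries no seriousness, relatedness or withdrawal attribute.

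**4. Reproducing the plan's precision figures.** Protocol 9.2.1 uses a Beta(1,1) prior, so x events in n patients give Beta(1+x, 1+n−x), with equal-tailed 95% limits.
- 1/15: Beta(2,15), limits 0.0155 to 0.3023 (plan: 0.02 to 0.30).
- 0/15: upper limit 1 − 0.025^(1/16) = 20.6% (plan: 21%).
- 2/15: upper limit 38.3% (plan: 38%).
- 0, 1 and 2 of 12: 24.7%, 36.0% and 45.5% (plan: 25%, 36%, 45%).

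These agree to rounding.

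**5. Effect of merging.** The event counts below are assumptions, all events are judged related, each is in a different patient, and n = 15.

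| Active only | Placebo only | Active lesion (upper limit) | Merged (upper limit) |
|---|---|---|---|
| 0 | 2 | 0/15 = 0% (20.6%) | 2/15 = 13.3% (38.3%) |
| 1 | 1 | 1/15 = 6.7% (30.2%) | 2/15 = 13.3% (38.3%) |
| 3 | 1 | 3/15 = 20.0% (45.6%) | 4/15 = 26.7% (52.4%) |
| 2 | 2 | 2/15 = 13.3% (38.3%) | 4/15 = 26.7% (52.4%) |

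The last two rows print the same total, although one has an excess on active and the other has none.

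**6. What a lesion-level comparison could show.** In an exact paired (McNemar) test with m discordant patients all in one direction, p = 2 × 0.5^m. That gives 0.0625 for m = 5 and 0.031 for m = 6, so at least six are needed for two-sided p < 0.05. With n = 15, independent lesions and assumed AE rates, power is 3% for 20% versus 5%, 26% for 40% versus 10%, and 49% for 50% versus 10%.

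**The case against.** A reader might infer that the tolerability objective loses its only controlled comparison. It does not. Tables 2.19 and 2.20 compare the two creams on irritation score, maximum dermal response and other dermal effects, and Listing 35 gives treatment and location. Scoring is scheduled in every visit column from Day 1 to Day 28 and again in Days 29 to 42. Protocol 12.3.1 also excludes signs and symptoms of the disease under study from the AE definition unless they are worse than expected, so the scored assessment is the main route for visible reactions. This stands, and it limits the gap to what the scores omit.

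A reader might also infer that placebo-lesion reactions will be counted as drug-related. They can be; it depends on the investigator's judgement for each event.

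Nor does it follow that Protocol 9.2.1 cannot be filled in. Every Group B patient receives active cream, so its column heading can be read as events in patients exposed to active, and patient totals would then serve. The active-lesion limits in step 5 apply only under the narrower reading.

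Three further points stand in part. No formal comparison is planned for the primary objective (Protocol 9.1), and overstating drug-related AEs errs on the cautious side. The AE shells and the AE form are not in the documents, so sequence or site could appear in Listing 14. With so few patients, a site named in the verbatim text (Listing 17) could be matched by hand to Listing 5. But that relies on chance wording, and no planned table does it.

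**Conclusion.** The concern holds for application-site AEs only. For these, the stated reason for dropping treatment does not apply, and active-lesion and placebo-lesion events are merged in Tables 2.1 to 2.4. What is lost is the lesion-level split of local AEs: chiefly itch, burning and pain, and the seriousness, relatedness and withdrawal attributes of any local AE. The comparison of visible signs is intact, and totals are right for systemic AEs.

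The size depends on how many local AEs fall on the placebo lesion, which the documents cannot tell us. In the assumed cases above, the merged count exceeds the active-lesion count by one or two patients in 15, and the upper limit rises by about 7 to 18 percentage points (52.4 − 45.6 = 6.8; 38.3 − 20.6 = 17.7). Any comparison would be descriptive.

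Separately, SAP 11.2.1 (by sequence) and SAP 11.8.5 (totals only) contradict each other for the AE tables. This is an inexpensive improvement, worth making before the data are frozen.

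**What to change.** Before database freeze and release of the randomisation codes (SAP 3.1):

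- Obtain the affected site (F, G, other or unknown) for each application-site AE, from the CRF if it is recorded there, otherwise by query to the site.
- Assign treatment from the randomisation schedule, as SAP 11.2.1 already does for local tolerability.
- Add one descriptive table beside Table 2.20: patients with application-site AEs on the active lesion only, the placebo lesion only, both, or unknown.
- Add site and treatment to Listing 14.
- Footnote placebo-lesion entries in Table 2.2, but do not remove them. Removal would overrule the investigator's causality judgement using the code. It would also presume that such a reaction is due to vehicle alone, although both lesions lie in one anatomical area and Protocol 4.5 reports that the drug reaches the circulation.
- Keep systemic AEs as totals, and reconcile the sequence wording in SAP 11.2.1 with the AE table notes in SAP 11.8.5.

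Cost: a few queries, one table, two listing columns and a footnote. The SAP describes some Group B data as already collected (8.3.2), so the queries may be retrospective and some events may remain unassignable; the unknown row allows for that. The documents do not show whether the eCRF already records the lesion for an AE.
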